1.1. Objectives, Endpoints, and Estimands

Objectives	Endpoints
Primary	

 To evaluate the bioequivalence of a 200-mg SC dose of 100 mg/mL citrate-free mirikizumab solution using a 1 × 2-mL AI (test) compared to using 2 × 1-mL AI (reference) 	
 C_{max}, $AUC_{(0-\infty)}$, and $AUC_{(0-t_{last})}$
Secondary	
 TEAEs and SAEs
Exploratory	
 
 To evaluate the impact of injection site location on PK

Abbreviations: AI = autoinjector; $AUC_{(0-\infty)}$ = area under the concentration versus time curve from time zero to infinity; $AUC_{(0-t_{last})}$ = area under the concentration versus time curve from time zero to time t , where t is the last time point with a measurable concentration; C_{max} = maximum observed drug concentration; PK = pharmacokinetics; SAE = serious adverse event; SC = subcutaneous; TEAE = treatment emergent adverse event.

1.2. Study Design

Study AMCB is a Phase 1, open-label, randomized, 2-arm, parallel-design, single-dose multi-center study of citrate-free mirikizumab administered via autoinjector (AI) in healthy participants.

Screening

All participants will be screened within 35 days prior to Day 1.

Treatment and assessment period

Eligible participants will be admitted to the clinical research unit (CRU) on Day -1. Participants will be stratified by 1 of 3 weight categories based on their weight assessment measured on Day -1:

- less than 75.0 kg
- 75.0 to 85.0 kg
- more than 85.0 kg

Participants will be stratified by weight category and randomized in 1:1 to either 1 × 2-mL subcutaneous (SC) injection of 100 mg/mL citrate-free mirikizumab (test) or 2 × 1-mL SC injections of 100 mg/mL citrate-free mirikizumab (reference) with a computer-generated allocation code using an interactive web-response system (IWRS). Injection site location, either arm, thigh, or abdomen, will be assigned in an approximately equal distribution within each study arm using an IWRS.

Approximately 440 participants will be enrolled to ensure 400 completers. Approximately 220 participants will be randomized to the test arm, and 220 participants will be randomized to the reference arm, with approximately 73 participants for each injection site in each study arm.

A minimum of approximately 73 participants overall in each weight category should complete the study.

On Day 1, participants will receive assigned study intervention. Participants may be allowed to leave the CRU after completing the 4-hour safety assessments on Day 1, or later at the investigator's discretion, and will return for PK sampling and safety assessments at predefined times up to 10 weeks postdose. Participants will be monitored for safety between outpatient visits by way of telephone assessment.

Safety will be assessed through clinical chemistry, hematology, urinalysis testing, vital signs measurements, recording of adverse events (AEs) and product complaints (PC), and physical examination.

2. Statistical Hypotheses

The primary objective of this study is to evaluate the bioequivalence of a single 2-mL SC dose of citrate-free mirikizumab solution in AI compared to 2 × 1-mL SC dose of citrate-free mirikizumab solution in AI.

3. Analysis Sets

The following analysis sets are defined:

Participant Analysis Set	Description
Enrolled	All participants randomly assigned to study intervention.
Safety analysis set	All participants who are exposed to study intervention. Participants will be analyzed according to the intervention they actually received.
PK analysis set	All enrolled participants who receive a full dose of study intervention and have evaluable PK data according to the study intervention actually received. Note: The full dose will be determined only when the CRF data for full dose information is available.

Abbreviations: CRF = case report form; PK = pharmacokinetics.

Participants may be excluded from the PK analysis set in the event of

- a device malfunction
- administration of only 1 of the $2 \times 1\text{-mL}$ AI doses, or
- administration of an incorrect or incomplete dose.

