9.2. Analyses Sets

Participant Analysis Set	Description
Enrolled	All participants randomly assigned to study intervention.
Safety analysis set	All participants who are exposed to study intervention. Participants will be analyzed according to the intervention they actually received.
PK analysis set	All enrolled participants who receive a dose of study intervention and have evaluable PK data according to the study intervention actually received.

Participants may be excluded from the PK analysis set in the event of

- a device malfunction
- administration of only 1 of the 2 × 1-mL AI doses, or
- administration of an incorrect or incomplete dose.

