4.4.10. Hypersensitivity Reactions	17
4.4.11. Bleeding and Bruising Assessment.....	17
4.4.12. Other Assessments	18
4.4.13. Safety Statistical Methodology	18
4.5. Interim Analyses.....	18
4.6. Changes from the Protocol-Specified Statistical Analyses	18
5. Sample Size Determination	19
6. Data Presentation.....	20
6.1. Derived Parameters	20
6.2. Missing Data.....	20
6.3. Insufficient Data for Presentation.....	20

7. References	21
---------------------	----

Version history

This statistical analysis plan (SAP) for Study I6T-MC-AMCB (AMCB) is based on the protocol dated 21 March 2024.

SAP Version History Summary

SAP Version	Approval Date	Change	Rationale
1	See date on Page 1	Not Applicable	Original version

1. Introduction

This SAP has been developed after review of the clinical study protocol (final version dated 21 March 2024).

This SAP describes the planned analysis of the safety and pharmacokinetic (PK) data from this study. A detailed description of the planned tables, figures, and listings (TFLs) to be presented in the clinical study report (CSR) is provided in the accompanying TFL shell document. The intent of this document is to provide guidance for the statistical and PK analyses of data. In general, the analyses are based on information from the protocol. A limited amount of information concerning this study (for example, objectives, study design) is given to help the reader's interpretation.

This SAP must be finalized prior to first participant visit. When the SAP and TFL shells are agreed upon and finalized, they will serve as the template for this study's CSR.

This SAP supersedes the statistical considerations identified in the protocol; where considerations are substantially different, they will be so identified. If additional analyses are required to supplement the planned analyses described in this SAP, they may be performed and will be identified in the CSR. Any substantial deviations from this SAP will be identified in the CSR. Any minor deviations from the TFLs may not be documented in the CSR.

This SAP is written with consideration of the recommendations outlined in the International Conference on Harmonisation (ICH) E9 Guideline entitled "Guidance for Industry: Statistical Principles for Clinical Trials" (ICH 1998) and the International Conference on Harmonisation E3 Guideline entitled "Guidance for Industry: Structure and Content of Clinical Study Reports" (ICH 1995).

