4.1. General Considerations

Summary statistics and statistical analysis will only be presented for data where detailed in this SAP. For continuous data, summary statistics will include the arithmetic mean, arithmetic standard deviation (SD), median, minimum, maximum, and number of observations; for log-normal data (for example, the PK parameters: areas under the concentration versus time curve [AUCs] and maximum observed drug concentration [C_{max}]), the geometric mean and geometric coefficient of variation (CV%) will also be presented. For categorical data, frequency count and percentages will be presented. Data listings will be provided for all participants up to the point of withdrawal, including both scheduled or unscheduled visit results, with any participants excluded from the relevant population highlighted. Summary statistics and statistical analyses will generally only be performed for participants included in the relevant analysis population at scheduled visits only. For the calculation of summary statistics and statistical analysis, unrounded data will be used.

For change from baseline summary statistics, each individual change from baseline will be calculated by subtracting the individual participant's baseline value from the value at that timepoint, where baseline is defined as the last non-missing data up to the first dose. The individual participant's change from baseline values will be used to calculate the summary statistics (arithmetic mean, arithmetic SD, median, minimum, maximum, and number of observations) using a SAS procedure such as Proc Univariate.

Data analysis will be performed using SAS[®] Version 9.4 or greater.

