- Also, where two or more consecutive concentrations are BQL towards the end of a profile, the profile will be deemed to have terminated, and therefore, any further quantifiable concentrations will be set to missing for the calculation of the PK parameters unless it is considered to be a true characteristic of the profile of the drug.

Individual Concentration versus Time profiles

- Individual concentrations will be plotted utilizing actual sampling times.
- The terminal point selections will be indicated on a semi-logarithmic plot.

Average Concentration versus Time profiles

- The average concentration profiles will be graphed using scheduled (nominal) sampling times.
- The average concentration profiles will be graphed using arithmetic average concentrations.

- The pre-dose average concentration for single-dose data from non-endogenous compounds will be set to zero. Otherwise, only quantifiable concentrations will be used to calculate average concentrations.
- Concentrations at a sampling time exceeding the sampling time window specified in the protocol or $\pm 10\%$ will be excluded from the average concentration profiles.
- Concentrations excluded from the mean calculation will be documented in the final CSR.
- A concentration average will be plotted for a given sampling time only if 2/3 of the individual data at the time point have quantifiable measurements that are within the sampling time window specified in the protocol or $\pm 10\%$. An average concentration estimated with less than 2/3 but more than 3 data points may be displayed on the mean concentration plot if determined to be appropriate and will be documented within the final CSR.

Treatment of outliers during PK analysis

Application of this procedure to all PK analyses is not a requirement. Rather, this procedure provides justification for exclusion of data when scientifically appropriate. This procedure describes the methodology for identifying an individual value as an outlier for potential exclusion but does not require that the value be excluded from analysis. The following methodology will not be used to exclude complete profiles from analysis.

Data within an Individual profile

A value within an individual profile may be excluded from analysis if any of the following criteria are met:

- For PK profiles during single dosing of non-endogenous compounds, the concentration in a pre-dose sample is quantifiable.

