4.6. Changes from the Protocol-Specified Statistical Analyses

There were no changes from the protocol-specified statistical analyses.

5. Sample Size Determination

Approximately 440 participants, 220 participants in each treatment arm, may be enrolled so that approximately 400 participants, 200 in each test and reference group, complete the study.

Within each weight category, participants will be assigned to an SC injection site of either the arm, thigh, or abdomen, approximately 73 participants per injection site for the reference and test arms.

A sample size of 200 participants per treatment group will provide approximately 90% probability that the 90% CI of the geometric mean ratio of C_{max} and area under the concentration versus time curve between groups will fall within the equivalence boundary of 0.80 to 1.25. This sample size calculation was based on the assumptions that the coefficient of variation of PK parameters is up to 41.8% for each treatment group and the expected ratio of geometric means is between 0.9 and 1.1.

6. Data Presentation

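### Does the optional wording on PK-set exclusions in SAP Section 3 leave the 5% error rate of the bioequivalence test unprotected?

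*SAP*

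**What the plan says.** SAP Section 3 admits to the PK set "All enrolled participants who receive a full dose of study intervention and have evaluable PK data according to the study intervention actually received". A note adds: "The full dose will be determined only when the CRF data for full dose information is available". The list that follows opens with "Participants may be excluded from the PK analysis set in the event of" and names three events: a malfunctioning device, only one of the two 1-mL injections given, and an incorrect or incomplete dose.

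Protocol 9.2 carries the same list but defines the set as "All enrolled participants who receive a dose of study intervention and have evaluable PK data according to the study intervention actually received", so it asks for a dose and not a full dose. SAP Section 1 sets the order of precedence: "This SAP supersedes the statistical considerations identified in the protocol; where considerations are substantially different, they will be so identified". SAP 4.6 then records: "There were no changes from the protocol-specified statistical analyses".

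On reporting, SAP 4.1 provides listings "with any participants excluded from the relevant population highlighted", and SAP 4.4.1 lists product complaints. Neither document states when PK-set exclusions are decided.

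**The concern.** Read literally, SAP Section 3 treats the same person in two ways. Someone given one of two injections is outside the set by definition, yet the list makes the exclusion optional. Someone whose device malfunctioned but who received the full dose meets the definition, so only the optional wording applies. A blank full-dose field leaves a person unclassified.

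This matters more here than in most PK studies, because the trial compares autoinjectors and a malfunction is a feature of what is being compared. The study is open-label, the reference arm uses two devices per person, and a missed second injection can occur only in that arm. The 90% confidence interval rule caps the chance of a false bioequivalence claim at 5% only if membership does not depend on the results. If cases could be kept or dropped after the concentrations are seen, that cap would not hold.

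**Working it through.** **Inputs.** 200 per arm, CV up to 41.8%, expected ratio 0.9 to 1.1 and about 90% probability come from Protocol 9.5 and SAP 5. The 0.80 to 1.25 limits and the 90% interval come from SAP 4.3.2.1. The 5% level is implied by the interval and is not written down. No malfunction rate is given; Protocol 2.2.1 says only that earlier autoinjector use performed acceptably. All case counts below are assumptions.

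**The plan's own figure.** SD on the log scale = √ln(1 + 0.418²) = 0.4013. Standard error = 0.4013 × √(2/200) = 0.0401. At ratio 0.9, ln(0.9/0.8) = 0.1178, and 0.1178/0.0401 = 2.94. Subtracting 1.65 gives 1.29, and Φ(1.29) = 0.90. The exact calculation gives 90.1% at ratio 0.9 and 93.8% at 1.1, so the stated power is reproduced.

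**What the text does with each case.**

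| Case | Definition | List | Result |
|---|---|---|---|
| One of two injections, or incomplete delivery, recorded | Not a full dose | Optional | Out; the list is redundant |
| Malfunction, full dose delivered | Met | Optional | Left to judgement |
| More than 200 mg | Not clearly ruled out | Optional | Left to judgement; devices hold 100 or 200 mg (Protocol 6.1), so an extra device would be needed |
| Full-dose field blank | Not classified | None | Dosing is also recorded in source documents (Protocol 6.4) |

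**Error rate for a malfunction with full delivery.** The check simulated a two-group t-test on the log scale with 200 per arm and a true ratio of 0.80. It used 2,000,000 trials per cell, left out the site and weight terms, and assumed the malfunction does not alter exposure. The entry is the probability of a bioequivalence claim for one parameter.

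| Cases (test, reference) | All kept | All removed | Better of the two, chosen afterwards | Only unfavourable cases removed |
|---|---|---|---|---|
| 2, 0 | 0.0502 | 0.0503 | 0.0532 | 0.0545 |
| 5, 0 | 0.0502 | 0.0502 | 0.0548 | 0.0612 |
| 10, 0 | 0.0500 | 0.0500 | 0.0567 | 0.0744 |
| 5, 10 | 0.0501 | 0.0501 | 0.0582 | 0.0892 |

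Results at 1.25 agree within 0.1 point. A separate run of 400,000 trials per cell gave 5.2–5.3% for a single case in one arm with the better result chosen afterwards.

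Hand check of 0.0744: on average 5 of the 10 test cases fall below the arm mean, by 0.798 SD each. Removing them shifts the log ratio by 5 × 0.798 × 0.4013/195 = 0.0082. The standard error is 0.4013 × √(1/195 + 1/200) = 0.0404, and 0.0082/0.0404 = 0.20. Then 1 − Φ(1.645 − 0.20) = 0.074.

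**Power.** Removing ten test-arm cases by a fixed rule lowers power at ratio 0.9 from 90.0% to 89.4%.

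**A short dose that slips through a blank field.** Assume half exposure. That is ln 2/0.4013 = 1.73 SD below the mean, and one such person among 200 moves the ratio by 2^(1/200) = 1.0035, or 0.35%. Kept in the reference arm at a true ratio of 0.80, one such person gives 5.9% and ten give 20.1%. The ±3 SD outlier test would flag only about Φ(−3 + 1.73) = 10% of them. The protection against this case is therefore the full-dose definition, which removes them once the dosing record is read.

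**The case for a change.** The strongest case for a change is that nothing in the documents closes the timing gap. SAP 4.1 marks exclusions but does not date them. The outlier procedure offers no control, since "The following methodology will not be used to exclude complete profiles from analysis". The only text on approving exclusions, in SAP 4.3.1 for outlier values, ties approval to the final study report, after the results are known. The sponsor or its designee runs the analysis, and no text withholds concentrations from them. One paragraph of wording would settle the matter.

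The gap in wording stands. The step from it to a loss of error control does not. The full-dose note ties that status to case report form data and not to concentrations. Protocol 10.2 withholds PK results from the sites, so those who record the dose and the malfunction do not see the outcome. Product complaints not linked to a serious event are due within 1 business day of awareness (Protocol 8.3.1), so the facts are on file early. With complaints listed and excluded participants highlighted, a reader could match the two and see selective removal. These features give transparency and not a decision date, but they make the harmful use of the discretion visible.

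A stricter rule would also gain little. Fixing full-delivery malfunctions in or out gives 5.0% either way. Membership as a whole cannot be locked before concentrations are released, because evaluable data is part of the definition and SAP 4.3.1 judges AUC by the number of consecutive quantifiable values. A default of inclusion when the full-dose field is blank could keep an undocumented short dose.

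The difference between a dose and a full dose is clerical. The SAP was written against the protocol of 21 March 2024 and plans 440 participants, while the current protocol plans 484. Its statement of no changes refers to a version not available here, so only the current texts can be said to differ, and the SAP's definition prevails.

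**Conclusion.** No change to the plan is needed. The documents leave out a decision time, and the optional list overlaps the definition, but the plan followed as written gives a sound primary test. Recorded short doses are out, and a full-delivery malfunction carries a 5.0% error rate whether such cases are kept or removed.

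Inflation requires two further things that the documents neither state nor imply: an appreciable number of full-delivery malfunctions, and a choice made with concentrations in view. With 1 to 5 cases in one arm and an all-in or all-out choice, the rate is about 5.2–5.5%. The 8.9% figure needs 15 such cases with every unfavourable one, and no other, removed. All these rates are per parameter; if all three primary parameters must pass, the joint rate is no higher.

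The conclusion rests on the assumed case counts, a CV of 41.8%, exposure being unaffected when the full dose is recorded as delivered, and blank fields being resolved from source records. Settling dosing-related exclusions from those records before analysis is ordinary practice, and nothing in the plan prevents it.

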3.1. Treatments

Study Treatment Name	Injection Site	Abbreviation	Treatment order in TFL	
2 \times 1-mL SC injections of 100 mg/mL citrate-free mirikizumab (Reference)	Abdomen	CF Solution AI (Reference) (Abdomen)	1	3
	Arm	CF Solution AI (Reference) (Arm)		4
	Thigh	CF Solution AI (Reference) (Thigh)		5
1 \times 2-mL SC injections of 100 mg/mL citrate-free mirikizumab (Test)	Abdomen	CF Solution AI (Test) (Abdomen)	2	6
	Arm	CF Solution AI (Test) (Arm)		7
	Thigh	CF Solution AI (Test) (Thigh)		8

Abbreviations: AI = autoinjector; CF = citrate-free; SC = subcutaneous; TFL = table, figure, and listing.

Note: A TFL with only treatment arms order will be 1 and 2, while a TFL with treatment by injection site order will be 3, 4, 5, 6, 7, and 8, as shown in the above table.

4. Statistical Analyses

4.1. General Considerations

Summary statistics and statistical analysis will only be presented for data where detailed in this SAP. For continuous data, summary statistics will include the arithmetic mean, arithmetic standard deviation (SD), median, minimum, maximum, and number of observations; for log-normal data (for example, the PK parameters: areas under the concentration versus time curve [AUCs] and maximum observed drug concentration [C_{max}]), the geometric mean and geometric coefficient of variation (CV%) will also be presented. For categorical data, frequency count and percentages will be presented. Data listings will be provided for all participants up to the point of withdrawal, including both scheduled or unscheduled visit results, with any participants excluded from the relevant population highlighted. Summary statistics and statistical analyses will generally only be performed for participants included in the relevant analysis population at scheduled visits only. For the calculation of summary statistics and statistical analysis, unrounded data will be used.

For change from baseline summary statistics, each individual change from baseline will be calculated by subtracting the individual participant's baseline value from the value at that timepoint, where baseline is defined as the last non-missing data up to the first dose. The individual participant's change from baseline values will be used to calculate the summary statistics (arithmetic mean, arithmetic SD, median, minimum, maximum, and number of observations) using a SAS procedure such as Proc Univariate.

Data analysis will be performed using SAS[®] Version 9.4 or greater.

4.2. Demography and Participant Dispositions

Participant disposition will be listed. The demographic variables age, sex, race, ethnicity, country of enrolment, site ID, body weight, weight category, height, and body mass index will be summarized by treatment, and overall; the data will also be listed. All other demographic variables will be listed only.

4.3. Primary Endpoint(s) Analysis

4.3.1. Pharmacokinetic Analysis

PK parameter estimates will be determined using non-compartmental procedures in the validated software program (Phoenix WinNonlin Version 8.3.5).

Serum concentrations of mirikizumab will be used to determine the following PK parameters, when possible:

Parameter	Units	Definition
AUC _(0-t_{last})	day* μ g/mL	area under the concentration versus time curve from time zero to time t, where t is the last time point with a measurable concentration
t _{last}	Day	the last time point with a measurable concentration
AUC _(0-∞)	day* μ g/mL	area under the concentration versus time curve from time zero to infinity
%AUC _(t_{last}-∞)	%	percentage of AUC _(0-∞) extrapolated
C _{max}	μ g/mL	maximum observed drug concentration
t _{max}	day	time of maximum observed drug concentration
t _{1/2}	day	half-life associated with the terminal rate constant (λ_z) in non-compartmental analysis
CL/F	L/day	apparent total body clearance of drug calculated after extra-vascular administration
V _{Z/F}	L	apparent volume of distribution during the terminal phase after extra-vascular administration
V _{ss/F}	L	apparent volume of distribution at steady state after extra-vascular administration

Additional PK parameters such as weight-normalized PK parameter estimates may be calculated, as appropriate. The software and version used for the final analyses will be specified in the CSR. Any exceptions or special handling of data will be clearly documented within the final CSR.

Formatting of tables, figures, and abbreviations will follow the Eli Lilly Global PK/PD/TS Tool: NON-COMPARTMENTAL PHARMACOKINETIC STYLE GUIDE. The version of the tool effective at the time of PK analysis will be followed.

General PK parameter rules

- Actual sampling times will be used in the final analyses of individual PK parameters, except for non-bolus pre-dose sampling times, which will be set to zero. For non-bolus, multiple dose profiles, the pre-dose time will be set to zero unless a time deviation falls outside of the protocol blood collection time window which is considered to impact PK parameter derivation.
- C_{max} and t_{max} will be reported from observed values. If C_{max} occurs at more than one time point, t_{max} will be assigned to the first occurrence of C_{max}.
- AUC parameters will be calculated using a combination of the linear and logarithmic trapezoidal methods (linear-log trapezoidal rule). The linear trapezoidal method will be applied up to t_{max}, and then the logarithmic trapezoidal method will be used after t_{max}. The minimum requirement for the calculation of AUC will be the inclusion of at least three consecutive concentrations above the lower limit of quantification, with at least one

of these concentrations following C_{max} . $AUC_{(0-\infty)}$ values where the percentage of the total area extrapolated is more than 20% will be flagged. Any $AUC_{(0-\infty)}$ value excluded from summary statistics will be noted in the footnote of the summary table.

- Half-life ($t_{1/2}$) will be calculated, when appropriate, based on the apparent terminal log-linear portion of the concentration-time curve. The start of the terminal elimination phase for each participant will be defined by visual inspection and generally will be the first point at which there is no systematic deviation from the log-linear decline in serum concentrations. Half-life will only be calculated when a reliable estimate for this parameter can be obtained comprising of at least 3 data points. If $t_{1/2}$ is estimated over a time window of less than 2 half-lives, the values will be flagged in the data listings. Any $t_{1/2}$ value excluded from summary statistics will be documented in the footnote of the summary table.
- A uniform weighting scheme will be used in the regression analysis of the terminal log-linear portion of the concentration-time curve.
- The parameters based on observed last quantifiable drug concentration (C_{last}) will be reported.

Individual PK parameter rules

- Only quantifiable concentrations will be used to calculate PK parameters with the exception of special handling of certain concentrations reported below the lower limit of quantitation (BQL). Serum concentrations reported as BQL will be set to a value of zero when all of the following conditions are met:
 - The compound is non-endogenous.
 - The samples are from the initial dose period for a participant or from a subsequent dose period following a suitable wash-out period.
 - The time points occur before the first quantifiable concentration.
- All other BQL concentrations that do not meet the above criteria will be set to missing.
- Also, where two or more consecutive concentrations are BQL towards the end of a profile, the profile will be deemed to have terminated, and therefore, any further quantifiable concentrations will be set to missing for the calculation of the PK parameters unless it is considered to be a true characteristic of the profile of the drug.

Individual Concentration versus Time profiles

- Individual concentrations will be plotted utilizing actual sampling times.
- The terminal point selections will be indicated on a semi-logarithmic plot.

Average Concentration versus Time profiles

- The average concentration profiles will be graphed using scheduled (nominal) sampling times.
- The average concentration profiles will be graphed using arithmetic average concentrations.

- The pre-dose average concentration for single-dose data from non-endogenous compounds will be set to zero. Otherwise, only quantifiable concentrations will be used to calculate average concentrations.
- Concentrations at a sampling time exceeding the sampling time window specified in the protocol or $\pm 10\%$ will be excluded from the average concentration profiles.
- Concentrations excluded from the mean calculation will be documented in the final CSR.
- A concentration average will be plotted for a given sampling time only if 2/3 of the individual data at the time point have quantifiable measurements that are within the sampling time window specified in the protocol or $\pm 10\%$. An average concentration estimated with less than 2/3 but more than 3 data points may be displayed on the mean concentration plot if determined to be appropriate and will be documented within the final CSR.

Treatment of outliers during PK analysis

Application of this procedure to all PK analyses is not a requirement. Rather, this procedure provides justification for exclusion of data when scientifically appropriate. This procedure describes the methodology for identifying an individual value as an outlier for potential exclusion but does not require that the value be excluded from analysis. The following methodology will not be used to exclude complete profiles from analysis.

Data within an Individual profile

A value within an individual profile may be excluded from analysis if any of the following criteria are met:

- For PK profiles during single dosing of non-endogenous compounds, the concentration in a pre-dose sample is quantifiable.
- For any questionable datum that does not satisfy the above criteria, the profile will be evaluated, and results reported with and without the suspected datum.

Data between Individual profiles

1. If $n < 6$, then the dataset is too small to conduct a reliable range test. Data will be analyzed with and without the atypical value, and both sets of results will be reported.
2. If $n \geq 6$, then an objective outlier test will be used to compare the atypical value to other values included in that calculation:
 - a. Transform all values in the calculation to the logarithmic domain.
 - b. Find the most extreme value from the arithmetic mean of the log transformed values and exclude that value from the dataset.
 - c. Calculate the lower and upper bounds of the range defined by the arithmetic mean $\pm 3 \times \text{SD}$ of the remaining log-transformed values.

- d. If the extreme value is within the range of arithmetic mean $\pm 3 \times \text{SD}$, then it is not an outlier and will be retained in the dataset.
- e. If the extreme value is outside the range of arithmetic mean $\pm 3 \times \text{SD}$, then it is an outlier and will be excluded from analysis.

If the remaining dataset contains another atypical datum suspected to be an outlier and $n \geq 6$ following the exclusion, then repeat Step 2 above. This evaluation may be repeated as many times as necessary, excluding only one suspected outlier in each iteration, until all data remaining in the dataset fall within the range of arithmetic mean $\pm 3 \times \text{SD}$ of the log-transformed values.

Reporting of excluded values

Individual values excluded as outliers will be documented in the final CSR. Approval of the final CSR will connote approval of the exclusion.

